- Using a pilot randomized control trial with 30 mother-infant-caregiver triad (15 intervention, 15 control) determine the feasibility, acceptability, and preliminary efficacy of the adapted intervention compared to the original intervention. We hypothesize that the adapted intervention will be feasible, acceptable to study participants, and efficacious in addressing feeding styles and practices and caregivers' role in infant feeding.

We anticipate that the intervention will be feasible to deliver and acceptable to mothers and caregivers, and that the mother—infant-caregiver triads randomized to intervention with the adapted Healthy Beginnings curriculum compared to the treatment as usual control group will demonstrate greater improvements in outcomes (i.e., infant feeding knowledge and use of recommended feeding practices) after 6 months compared to the control group.

III – Study Design and Methodology

13. Study Timelines

Estimated start date for involvement of participants: February 1, 2023 or upon approval of the IRB protocol.

Estimated completion date for the involvement of participants: Feb. 28, 2024

14. Location of Research

a) Where will this study take place? If there is an online component, provide details.

(Max ¼ page)

The research will be carried out in Inland Southern California, specifically communities of the Coachella Valley and surrounding area. The PI, [name] and Co-Investigator [name], along with graduate and undergraduate research assistants are located at UCR. Co-I, [name], and research coordinator/assistant, [name], is located at Brown University. Community Investigator, [name], is located in the Coachella Valley. All research takes place at UCR. The research will primarily engage Latinx and Indigenous Mexican (e.g., Purépecha) communities in Inland southern California.

b) Is this a collaborative or multi-site study? Yes No

- Collaborative or cooperative studies involve investigators from two or more institutions working together to conduct a research project. Different research activities can occur at different sites or the study can be a single-site study that involves personnel from multiple institutions.
- Multi-site studies use the same research procedures outlined in a single protocol that is carried out at multiple institutions (e.g., a clinical trial where participants will be enrolled at each participating site, or an educational intervention implemented at each participating site).

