provides medical care to patients on the 2nd Saturday of the month in Mecca, CA. [name] is faculty supervisor of this clinic and [name] oversees a team of community health workers that support the clinic. As described below, infant anthropometric measurements will be collected at this clinic. A letter of access signed by [name], the primary faculty supervisor, is included as an appendix (see Appendix B– Healthcare Systems - Access Letters of Support). Once additional letters are obtained from our healthcare systems partners, we will submit the access letters to the IRB for review.

15. Participant Population: Please describe the participants/subjects. List the inclusion/exclusion criteria. Include any age, language, gender, or race-related inclusion/exclusion criteria and provide a justification for the use of these criteria. If applicable, please provide a rationale for your choice in sample size and/or sample size calculation.

If you are conducting research in languages other than English, translated versions of the participant-facing research materials (e.g., informed consent, recruitment materials, measures, etc.) must be submitted for review along with the [Certificate of Translation form](#).

(Max ¼ page)

Latina mothers, their infant, and their identified caregivers will be part of the intervention study. Mothers will be eligible if they 1) identify as Latina, 2) 18 years or older, 3) speak English, Spanish or Purépecha; 4) mother (biological, adoptive, foster) of an infant ages 4 months or younger, who had a normal birth weight (greater than or equal to 5 lbs., 8 oz.), 5) live in Inland Southern California; 6) income eligible (mothers or their children) for government programs such as WIC, Early Head Start, MediCal, CalFresh and similar programs, 7) willing to have a community health worker enter your home to provide 30-45 minute in person sessions once per month over 6 months, 8) have another caregiver 18 years or older who participates in at least 3 hours of care per week and agrees to participate in the home sessions. We anticipate a sample of 30 mothers-infants-caregiver triads in the study, totaling 90 participants.

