participant's preference; each survey will last about 30-45 minutes. The survey will collect data on sociodemographic questions (e.g., income, education, language, mental health), infant feeding practices using the validated Infant Feeding Scale Questionnaire (Thompson et al., 2009), communication skills and conflict resolution strategies around feeding between the mother and other caregiver, and questions about breastfeeding, formula feeding, and family mealtimes (see *Appendix L. Pretest and Posttest Survey for Caregivers* and *Appendix M. Pretest and Posttest Survey for Mothers*). All participants (mothers and caregivers) will receive \$75 for completion of the pretest data collection and \$125 for completion of the posttest data collection. The purpose of an increased amount from baseline to follow-up is to compensate participants for the completion of the brief satisfaction surveys throughout the study and retain participants in the study over six months. (While only Group A participants will complete the brief satisfaction surveys, for purposes of equity all participants will receive \$125 at the end of the study.) In the final week of the study (week 24), study team members will administer the posttest surveys. The posttest survey will include the same questions as the pretest survey except it will not include the socio-demographic questions and will include a satisfaction survey. Only participants assigned to Group A – Grow Well will respond to the satisfaction survey questions. Participants can refuse to answer or skip any questions in either the pretest or posttest survey. If participants exit out of the study, their data will be removed from analysis.

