Satisfaction. Throughout the delivery of the intervention, the study team will determine the satisfaction with the intervention among participants in the intervention group (i.e., Group A- Grow Well) using brief surveys to assess mothers' and caregivers' perceptions of and satisfaction with the adapted curriculum. For the Grow Well group, after each in-person session and phone call check-in, the CHWs will provide participants with a QR code to access a brief satisfaction survey that will take about 5 minutes to complete. *Appendix W*. Brief Satisfaction Surveys includes both the survey to assess satisfaction after the in-home session and the survey to assess satisfaction after the phone call check ins. Additionally, at the completion of the intervention, study team members will conduct interviews with 15-20 participants (mothers and caregivers) in the intervention group (i.e., Group A- Grow Well). The interviews will assess perceptions of and satisfaction with the curriculum received. The interview will include open-ended questions about content, format, length, and cultural relevance of the curriculum (see *Appendix R*. Participant Satisfaction Interview). Study team members will conduct the interview by phone or Zoom after completion of the six-month study period. These interviews will be 30-45 minutes, audio recorded, and analyzed using rapid analytic techniques of template and matrix analysis as well as inductive approaches using MAXQDA qualitative analysis software. Participants will receive a gift card of \$25 for their time.

References

b) If you are using a dataset, please list out the variables you will be accessing. If you are using the Psychology Subject Pool, please list out the pre-screening data you will be collecting on your participants.

(Max ½ page)

NA

21. Deception

a) Does this study involve deception or intentional lack of disclosure?

Yes No

b) If YES, justify and indicate how participants will be debriefed. Indicate if participants are free to withdraw or selectively edit data after being fully debriefed. If NO, skip to the next question.

(Max ¼ page)

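### No rating or reason is sought when a Group A member stops, and leavers' earlier ratings are removed, so acceptability rests on those who stay enrolled

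*Protocol*

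**What the plan says.** Protocol section 12 makes acceptability a hypothesis: "We hypothesize that the adapted intervention will be feasible, acceptable to study participants". Section 20(a) repeats it as an aim of the pilot. Three instruments measure it, all in Group A only.

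- **Brief surveys** (section 20(a), Satisfaction): "after each in-person session and phone call check-in, the CHWs will provide participants with a QR code to access a brief satisfaction survey".
- **Satisfaction items in the posttest** (section 20(a), Baseline and follow up data collection): "In the final week of the study (week 24), study team members will administer the posttest surveys".
- **Open-ended interviews** on content, format, length and cultural relevance (section 20(a), Satisfaction): "at the completion of the intervention, study team members will conduct interviews with 15-20 participants (mothers and caregivers) in the intervention group". On timing: "Study team members will conduct the interview by phone or Zoom after completion of the six-month study period". Section 18 adds that interviewees opt in and are then selected.

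On people who leave, section 20(a) says that the data of those who exit are taken out of the analysis. Section 25 says that once a withdrawal is confirmed, everything collected from that person is destroyed and left out of analyses and deliverables. Sections 23(a) and 25 also say, more loosely, that a participant may opt out and ask for their data not to be used.

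The text available describes no exit interview, no question on the reason for stopping and no satisfaction rating at that time.

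**The concern.** People who find home visits too long, intrusive or ill-suited are among those most likely to stop. If they are not asked when they stop, and the ratings they gave before leaving are deleted, the acceptability result describes a group from which the dissatisfied have been filtered out. The bias probably runs upward.

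The pilot would also lose the reasons for stopping, which it most needs before a larger trial. The interview is the only instrument described as probing such reasons with open questions, and it comes last. For someone who stops after month 2 it would come about 6 - 2 = 4 months later, if they are still enrolled.

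An analysis plan cannot repair this. It concerns when questions are asked and which answers are kept.

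**Working it through.** **Inputs from the protocol.** The plan is "We anticipate a sample of 30 mothers-infants-caregiver triads in the study, totaling 90 participants", with 15 triads per arm. Each triad is one mother, one caregiver and one infant. Sessions and calls are each monthly for six months, and the calls are with mothers only (section 20(a)).

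**The plan's own figure.** 30 triads × 3 = 90 participants, which reproduces. Group A adults who can give ratings: 15 × 2 = 30. The 15-20 interviews cover 15/30 = 50% to 20/30 = 67% of them.

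**Brief-survey occasions.** A mother has up to 6 sessions + 6 calls = 12, and a caregiver about 6. By the end of month 2 a mother has been offered up to 2 + 2 = 4 and a caregiver up to 2.

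**What each kind of participant contributes to the analysed data:**

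| Group A adult | Brief surveys | Week-24 items | Interview | Asked when stopping |
|---|---|---|---|---|
| Takes part throughout | all occasions | yes | if opting in and selected | not applicable |
| Stops sessions or calls, stays enrolled | occasions before stopping | not excluded | not excluded | no |
| Exits or withdraws | given, then removed or destroyed | no | no provision | no |

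The last row drops out of the acceptability data altogether. The middle row keeps its early ratings but is not asked about the decision to stop when it happens.

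**Illustration 1 (all rates assumed).** Let *f* be the fraction who stop and contribute nothing to the analysis, with 91.7% of stayers and 33.3% of stoppers satisfied. The rate among everyone allocated is 0.917(1 - *f*) + 0.333*f*. The overstatement is *f* × (0.917 - 0.333) = 0.584*f*.

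- *f* = 0.10: everyone 86%, stayers 92%, overstatement 5.8 points
- *f* = 0.20: everyone 80%, stayers 92%, overstatement 11.7 points
- *f* = 0.30: everyone 74%, stayers 92%, overstatement 17.5 points

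**Illustration 2 (bounds).** Assume whole triads leave and about 90% of those remaining are satisfied. Count all leavers as dissatisfied for the lower bound and all as satisfied for the upper.

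- 2 triads lost (4 adults): 23/26 = 88% observed; among all 30, 23/30 = 77% to 27/30 = 90%
- 3 triads lost (6 adults): 22/24 = 92% observed; 22/30 = 73% to 28/30 = 93%
- 4 triads lost (8 adults): 20/22 = 91% observed; 20/30 = 67% to 28/30 = 93%

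With 30 adults, losing a few triads leaves a range too wide to settle the hypothesis.

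**The case against.** A reader might infer that those who stop are never heard, or that only completers can be interviewed. The protocol does not support either reading.

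- Satisfaction is sampled throughout delivery. A mother who stops after month 2 would already have been offered up to four brief surveys.
- The interview wording fixes a time, not a completion condition. Neither section 18 nor the opt-in wording in section 23(a) requires attendance.
- The posttest satisfaction items go to those assigned to Group A. Someone who stops home visits but stays enrolled may still answer them and be interviewed.

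It can also be said that the percentages rest on assumed rates and that the interviews are analysed qualitatively, so they yield no rate to overstate. Community health worker debriefs also cover retention, and the interview and survey appendices are not available to read.

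All of this stands, and it narrows the point. Two things remain. Early surveys rate sessions that were attended, not the decision to stop or its reason. And for those who exit or withdraw, even these ratings are lost under sections 20(a) and 25. The debriefs are three second-hand accounts from the people who delivered the programme. A qualitative result can be selected in the same way as a percentage.

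The opt-out wording in sections 23(a) and 25 might be read as deleting data only on request. However, the removal statement in section 20(a) and the destruction statement in section 25 carry no such condition.

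**Conclusion.** The point holds in this form. Group A members can rate sessions and calls while they take part, but nothing is asked when they stop, and leavers' earlier ratings do not survive into the analysis. The analysed acceptability data therefore come only from people who stay enrolled, and they probably overstate acceptability.

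The direction rests on the assumption that leavers are less satisfied than stayers, which is plausible but not shown. The size is unknown. The range of about 6 to 18 points follows only from the assumed 92% and 33% satisfaction rates with 10% to 30% stopping. It also treats every stopper as lost to the analysis, which is true of those who exit or withdraw but not of those who stop sessions and stay enrolled. The change should be made, but the pilot is not invalid without it.

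**What to change.** 1. In section 20(a), Satisfaction, state that any Group A mother or caregiver who stops sessions, calls or the study is offered, voluntarily and at that time, the posttest satisfaction items and the existing satisfaction interview. Reserve some of the existing 15-20 interview slots for those willing to take part.
2. Amend sections 20(a), 23(a) and 25 and the consent forms so that ratings already given, and any exit feedback, are kept when the participant agrees and destroyed only on an explicit request. Without this, exit feedback from people who leave the study would itself be deleted.
3. Report acceptability with the number of Group A adults allocated (30 planned), the number who stopped and the number not reached.

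The interview guide, staff, gift card and slots already exist. The cost is a small protocol and consent amendment. Some stoppers will decline, and slightly fewer completers will be interviewed.

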****Final decision of whether an IRB application is minimal risk or higher is up to the IRB****

c) 30. Provide a list of appendices here for all additional materials submitted with this IRB application (e.g., Appendix A – Informed Consent; Appendix B – Interview Guide; Appendix C – References, Appendix D – Recruitment flyers/materials; Appendix E – Access letters). The list should be in the same order as you append the materials at the end of the document with headers for ease of review and referencing.

[figure not shown]
